## 8.4.2 Serious Adverse Events

All SAEs, regardless of causality, must be reported to organization delegated by the Sponsor (Primevigilance will handle SAE reporting for INS-212) on a Serious Adverse Event Report Form within 24 hours of becoming aware of the event; corrections and additions are required to be submitted within 24 hours. Study-specific email, phone, and fax number for SAE reporting are presented in the Study Reference Manual.

Unexpected drug-related SAEs as assessed by Sponsor or authorized person qualify for expedited reporting and will be reported to the IRB/EC, regulatory authorities, participating Investigators and, if cross reporting is required for suspected unexpected serious adverse reactions (SUSARs), in accordance with all applicable global laws and regulations. A SUSAR is a Serious Adverse Reaction, which is suspected to be caused by the investigational medicinal product and which is unexpected i.e. its nature or severity is not consistent with the information in the relevant source documents. SAEs, including those that do not meet requirements for expedited reporting, and all other AEs will be reported to the regulatory agencies as appropriate (i.e. for the FDA these are reported in the Investigational New Drug [IND] annual report and for EMA these are reported in the Drug Safety Update Report ([DSUR]).

### 8.4.2.1 Pregnancy

Any pregnancy that occurs during any phase of the study must be reported to Prime Vigilance within 24 hours of learning of the pregnancy using a Clinical Study Pregnancy Form.

The study treatment should be discontinued and the pregnancy should be followed to term. The details of termination must also be reported, including details of birth, the presence or absence of birth defects, congenital abnormalities or maternal and newborn complications, or whether termination was spontaneous or voluntary.

### 8.4.2.2 Overdose

An overdose is defined as a dose greater than the dose level evaluated in this study as described in [Section 5](#) that results in clinical signs and symptoms. In the case of an overdose of study drug,

Protocol Amendment #3 version: 22 February 2016

*This protocol is solely for the purpose of communicating information about the investigational drug between Insmmed Incorporated and study personnel. Information is not to be reproduced, abstracted or used for sharing of information for any other purpose, whatsoever, except with the written permission of Insmmed Incorporated.*

the Investigator should use clinical judgment in treating the overdose and contact the study Medical Monitor. The Investigator should refer to the relevant document(s) for detailed information regarding warnings, precautions, contraindications, adverse events, and other significant data pertaining to the study drug used in the study. Such document(s) may include, but not limited to, the Investigator's brochure for LAI and approved product labeling for Amikacin.

## **8.5 FOLLOW-UP OF ADVERSE AND SERIOUS ADVERSE EVENTS**

All SAEs, including those ongoing at end-of-study, must be followed until resolution or stabilization or until otherwise explained.

## **8.6 REGULATORY ASPECTS**

The Sponsor has a legal responsibility to notify the FDA, National Competent Authorities and Central Ethics Committees of the European Union, and all other foreign regulatory agencies, as well as all sites, about the safety of the drug. The Investigator has the responsibility to notify the local EC about SUSARs.

The Investigator(s)/institution(s) will permit study-related monitoring, audits, IRB/EC review and regulatory inspection(s), providing direct access to source data/documents. Copies of the notification to the ethics committee must be sent to the Sponsor.

## **9 STATISTICS**

### **9.1 SAMPLE SIZE**

The sample size was determined for the primary comparison between the treatment arms LAI plus a multi-drug regimen and a multi-drug regimen alone with respect to the proportion of subjects achieving culture conversion by Month 6 using nQuery Advisor® 7.0. Assuming a culture conversion rate by Month 6 of no less than 20% for the LAI plus a multi-drug regimen treatment arm, the rate by Month 6 of 5% for the multi-drug regimen alone treatment arm, and a 2:1 randomization ratio, a sample size of 261 subjects (174 for LAI plus a multi-drug regimen and 87 for the multi-drug regimen) will provide at least 90% power for the continuity-corrected Chi-square test at the 2-sided significance level of 0.05.

Protocol Amendment #3 version: 22 February 2016

*This protocol is solely for the purpose of communicating information about the investigational drug between Insmmed Incorporated and study personnel. Information is not to be reproduced, abstracted or used for sharing of information for any other purpose, whatsoever, except with the written permission of Insmmed Incorporated.*

The sample size was also evaluated for the secondary endpoint of change from Baseline to Month 6 in 6MWT distance. Assuming a common standard deviation of 100 and a 2:1 randomization ratio to either LAI plus a multi-drug regimen or a multi-drug regimen alone, a sample size of 192 subjects (128 for LAI plus a multi-drug regimen and 64 for the multi-drug regimen) will provide at least 90% power to detect a between-treatment difference of 50 meters in mean change from Baseline to Month 6 in 6MWT distance using a two arm t-test at the 2-sided significance level of 0.05.

Due to lack of durability data, it is difficult to estimate the power with a total sample size of 261 subjects for the comparison between treatment arms with respect to the proportion of subjects achieving culture conversion with durability after 3 months off-treatment. Assuming the proportion of subjects achieving culture conversion with durability is 16% and 4% for LAI plus a multi-drug regimen and a multi-drug regimen respectively, and a 2:1 randomization ratio, a sample size of 261 subjects (174 for LAI plus a multi-drug regimen and 87 for the multi-drug regimen) will provide at least 83% power for Fisher's exact test at the 2-sided significance level of 0.05.

## **9.2 STRATIFICATION**

Subjects will be stratified by smoking status (current smoker or not) and prior multi-drug regimen (on treatment or off treatment for at least 3 months) at Screening.

## **9.3 RANDOMIZATION AND BLINDING**

Eligible subjects will be randomized 2:1 to open-label treatment with LAI plus a multi-drug regimen or a multi-drug regimen alone.

## **9.4 STATISTICAL METHODOLOGY**

A statistical analysis plan (SAP) will be developed describing details regarding all analyses, tables, figures, and data listings. All analyses will be performed using SAS®.

Protocol Amendment #3 version: 22 February 2016

*This protocol is solely for the purpose of communicating information about the investigational drug between Insmmed Incorporated and study personnel. Information is not to be reproduced, abstracted or used for sharing of information for any other purpose, whatsoever, except with the written permission of Insmmed Incorporated.*

The final analyses of the primary efficacy endpoint, the change from Baseline to Month 6 in 6MWT distance, and time to culture conversion by Month 6 will be performed when the last subject completes Month 6 and data for all subjects who have completed Month 6 are available. These final analyses will be performed prior to the completion of the study. Interim analysis of some safety data will be included.

## **9.5 ANALYSIS POPULATIONS**

### **9.5.1 Intent-to-treat Population**

The intent-to-treat (ITT) population is the set of all randomized subjects.

### **9.5.2 Per-protocol Population**

The per-protocol (PP) population is a subset of the ITT subjects who received at least 1 dose of either LAI plus a multi-drug regimen or a multi-drug regimen, met the inclusion/exclusion criteria, and did not have major protocol violations.

### **9.5.3 Safety Population**

The safety population is the set of all subjects who received at least 1 dose of either LAI plus a multi-drug regimen or a multi-drug regimen.

### **9.5.4 Pharmacokinetic Population**

The PK population is the set of all randomized subjects who received at least 1 dose of study drug and provided at least 1 PK sample.

## **9.6 EFFICACY ANALYSIS**

### **9.6.1 Primary Endpoint Analysis**

The primary efficacy endpoint is the proportion of subjects achieving culture conversion by Month 6. The primary efficacy analysis will be performed for the ITT population using the Cochran-Mantel-Haenszel test stratified by smoking status and prior multi-drug regimen (on treatment or off treatment for at least 3 months) at the 2-sided significance level of 0.05. The

Protocol Amendment #3 version: 22 February 2016

*This protocol is solely for the purpose of communicating information about the investigational drug between Insmad Incorporated and study personnel. Information is not to be reproduced, abstracted or used for sharing of information for any other purpose, whatsoever, except with the written permission of Insmad Incorporated.*

null hypothesis assumes that the culture conversion by Month 6 is independent of treatment, and the alternative hypothesis assumes that the culture conversion by Month 6 is associated with treatment. Subjects with missing sputum culture results for which culture conversion cannot be evaluated (3 consecutive monthly negative sputum cultures) will be considered as non-converters.

A supportive analysis of the primary efficacy endpoint will be performed for the PP populations similarly using the Cochran-Mantel-Haenszel test stratified by smoking status and prior multi-drug regimen.

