**Table 3-1 Schedule of Events**

INS-212	Screening	TREATMENT PHASE											OFF-TREATMENT PHASE									
		Baseline	Month 1 a	Month 2 a	Month 3	Month 4	Month 5 a	Month 6	Month 8	Month 10	Month 12	Month 14	EOT up to Month 16	28 Day Safety Follow-Up	3 Month Safety Follow-Up	6 Month Safety Follow-Up	EOS (12 Month Safety Follow-Up)					
		(V1)	(V2)	(V3)	(V4)	(V5)	(V6)	(V7)	(V8)	(V9)	(V10)	(V11)	(V12)	(V13)	(V14)	(V15)	(V16)	(V17)				
Visit Window	Approximately -98 to -70 (10-14 weeks) b	Day 1	(±3)	(±3)	(±3)	(±3)	(±3)	(±3)	(±3)	(±3)	(±3)	(±3)	(±3)	(±5)	(±5)	(±5)	(±5)	(±5)	(±7)	(±7)	(±7)	(±7)
Informed consent	X	-	-	-	-	-	-	-	-	-	-	-	-	-	-	-	-	-	-	-	-	-
Pregnancy test c	X	X	X	X	X	X	X	X	X	-	X	-	X	-	-	-	-	-	-	-	-	-
ECG	X	-	-	-	-	-	-	-	-	-	-	-	X	-	-	-	-	-	-	-	-	-
SGRQ	-	X	-	-	X	-	-	X	X	-	X	-	X	-	-	X	-	X	-	-	-	-
EQ-5D-3L	-	X	-	-	X	-	-	X	X	-	X	-	X	-	-	X	-	X	-	-	-	-
Medical history	X	X	-	-	-	-	-	-	-	-	-	-	-	-	-	-	-	-	-	-	-	-
Physical examination	X	X			X	X		X	X	-	X	-	X	-	-	X	-	X	-	-	X	X
Vital signs and pulse oximetry	X	X d			X d	X d		X d	X d	-	X d	-	X	-	-	X	-	X	-	-	X	X
6 minute walk test e	-	X	-	-	-	X	-	X	X	-	-	-	X	-	-	X	-	X	-	-	-	-

Protocol Amendment #3 version: 22 February 2016

*This protocol is solely for the purpose of communicating information about the investigational drug between Insmid Incorporated and study personnel. Information is not to be reproduced, abstracted or used for sharing of information for any other purpose, whatsoever, except with the written permission of Insmid Incorporated.*

Confidential

INS-212	Screening	TREATMENT PHASE											OFF-TREATMENT PHASE									
		Baseline	Month 1 a	Month 2 a	Month 3	Month 4	Month 5 a	Month 6	Month 8	Month 10	Month 12	Month 14	EOT up to Month 16	28 Day Safety Follow-Up	3 Month Safety Follow-Up	6 Month Safety Follow-Up	EOS (12 Month Safety Follow-Up)					
		(V1)	(V2)	(V3)	(V4)	(V5)	(V6)	(V7)	(V8)	(V9)	(V10)	(V11)	(V12)	(V13)	(V14)	(V15)	(V16)	(V17)				
Visit Window	Approximately -98 to -70 (10-14 weeks) b	Day 1	(±3)	(±3)	(±3)	(±3)	(±3)	(±3)	(±3)	(±3)	(±3)	(±3)	(±3)	(±5)	(±5)	(±5)	(±5)	(±5)	(±7)	(±7)	(±7)	(±7)
Pulmonary Function Tests f (FEV 1 [L], FEF (25-75%) , FVC)	-	X	-	-	-	-	-	X	-	-	-	-	-	-	-	-	-	X	-	-	-	-
Audiology test	X g	-	-	X	-	-	X	-	-	X	-	X	-	X	-	-	-	-	-	-	-	-

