## **3.6 DISCUSSION OF STUDY DESIGN**

### **3.6.1 Number of Subjects**

The study is designed to enroll enough subjects to ensure at least 261 evaluable subjects reach Month 6. Accounting for discontinuation, it is anticipated that up to approximately 351 randomized subjects may be required. An evaluable subject is one who has at least 1 sputum culture result at Baseline (Day 1) and for each month through Month 6.

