## 4.1 INCLUSION CRITERIA

To be eligible for enrollment, a prospective patient must meet all of the following criteria:

1. be male or female, 18 years or older (20 years or older in Japan)
2. be positive for MAC on culture as defined in inclusion criterion No. 4 while being treated with a multi-drug treatment regimen (at least 2 antibiotics) for a minimum duration of 6 consecutive months that is either ongoing or was stopped no more than 12 months before Screening (exceptions to multi-drug treatment regimen for 6 consecutive months include treatment with doses or frequencies below those recommended by guidelines and/or short interruptions of therapy, both occurring due to safety/tolerability issues)
3. be diagnosed with MAC NTM lung infection with evidence of underlying lung disease such as nodular bronchiectasis and/or fibrocavitary disease by chest radiography or chest computed tomography. High resolution CT (HRCT) scan is preferred, if available
4. have a MAC lung infection documented by at least 2 positive cultures (MAC or mixed infection with MAC as the dominant species), consisting of at least one obtained within 6 months prior to Screening and one positive culture at Screening (cultures to be at least 1 month apart). Cultures may be obtained from sputum or bronchoscopy.
5. have a MAC-positive sputum at Screening
6. be willing to adhere to multi-drug treatment regimen during the course of the study
7. be able to produce approximately 3 mL of sputum or be willing to undergo an induction that produces approximately 3 mL of sputum for mycobacteriology
8. female of child bearing potential agrees to practice an acceptable method of birth control (e.g., true abstinence [refraining from heterosexual intercourse during the entire study], hormonal or barrier methods, partner sterilization, or intrauterine device [IUD]) while participating in the trial. Periodic abstinence (e.g., calendar, ovulation, symptothermal, post-ovulation methods), declaration of abstinence for the duration of the study, and withdrawal are not acceptable methods of contraception.

Protocol Amendment #3 version: 22 February 2016

*This protocol is solely for the purpose of communicating information about the investigational drug between Insmmed Incorporated and study personnel. Information is not to be reproduced, abstracted or used for sharing of information for any other purpose, whatsoever, except with the written permission of Insmmed Incorporated.*

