#### **4.6 DEFINITIONS OF CONVERTER AND COMPLETER**

A converter is defined as a subject who has 3 consecutive monthly MAC-negative sputum cultures at any time within the first 6 months of the study.

Relapse or recurrence is defined as having MAC-positive sputum cultures in liquid broth media (agar negative) for 3 or more consecutive months, or having 1 MAC-positive sputum culture on solid media (agar positive) after achieving culture conversion.

A non-converter is defined as a subject who does not have 3 consecutive monthly MAC-negative sputum cultures at any time within the first 6 months of the study.

A completer for this study will be defined as follows:

1. A converter who successfully completes 12 months on the same treatment regimen beginning from the first of 3 negative cultures that defined conversion and successfully completes the 12 months off-treatment EOS follow-up visit.
2. A non-converter who successfully completes all dosing and protocol requirements up to and including the Month 6 study visit.

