## 6.2 BASELINE VISIT (DAY 1, VISIT 2)

All of the following should be performed or obtained within 70 days after Screening unless the results of the sputum culture analysis are delayed. In the event that sputum culture results are not known by 8 weeks (Day -14), the Baseline (Day 1) visit should be scheduled as soon as possible in order to maintain the Screening window, and an extension of the Screening window to 14 weeks is allowed, if necessary. If sputum culture results are known prior to 8 weeks (Day -14), the Screening window of 10 weeks must be maintained.

- administer SGRQ before study drug administration (see [Section 7.3.1](#))
- administer EQ-5D-3L before study drug administration (see [Section 7.3.2](#))
- collect information on healthcare resource utilization
- update medical history
- administer physical examination, including vital signs and pulse oximetry. Only vital signs and pulse oximetry will be assessed both before and after study drug administration (see [Section 7.2.2](#) and [Section 7.2.3](#))
- administer 6MWT (see [Section 7.2.1](#))

Protocol Amendment #3 version: 22 February 2016

*This protocol is solely for the purpose of communicating information about the investigational drug between Insmid Incorporated and study personnel. Information is not to be reproduced, abstracted or used for sharing of information for any other purpose, whatsoever, except with the written permission of Insmid Incorporated.*

- administer the pulmonary function test prior to study drug administration (see [Section 7.2.4](#))
- administer audiology test (may be administered either at the Screening or Baseline [Day 1] visit, not both; see [Section 7.2.9](#))
- obtain CT chest scan if part of CT Scan Sub-Study and has not been acquired within 6 months before Day 1 (see [Section 7.3.4](#), [APPENDIX 4](#))
- obtain CT chest scan if part of Japan specific CT Scan Sub-Study and has not been acquired within 6 months before Day 1 (see [APPENDIX 5](#))
- solicit concomitant medications (see [Section 7.2.8](#))
- assess AEs (see [Section 8](#))
- collect sputum specimen for microbiological assessment (see [Section 7.1.1](#))
- collect sputum specimen for sputum-only PK sub-set analyses (see [Section 7.4.1](#))
- collect blood or urine specimens for clinical chemistry, hematology, and urinalysis testing and, for women of child-bearing, a urine pregnancy test (see [Section 7.2.7](#))

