## **7.3.3 Identification of New or Different MAC Strains**

### **7.3.3.1 Methodology**

In subjects who convert (i.e., who have 3 consecutive monthly negative MAC sputum cultures) and who subsequently have a positive MAC sputum culture, analyses will be conducted to confirm whether the positive MAC culture is due to a different MAC species or strain acquired by the subject, or due to a relapse of the same MAC species or strain as observed at Baseline (Day 1). The MAC species will be identified by sequencing the gene for the 16S rRNA subunit.

Protocol Amendment #3 version: 22 February 2016

*This protocol is solely for the purpose of communicating information about the investigational drug between Insmmed Incorporated and study personnel. Information is not to be reproduced, abstracted or used for sharing of information for any other purpose, whatsoever, except with the written permission of Insmmed Incorporated.*

If the MAC isolates identified after conversion are a different species, it will be determined that the subject acquired a different MAC species, rather than having a relapse. If the same species as seen at Baseline (Day 1) is observed, then DNA fingerprinting (based on a variable number of tandem repeat) will be conducted to identify the strain to determine whether the subject has acquired a different MAC strain.

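### The primary CMH test leaves out the pre-dose Day 1 culture, so subjects already culture-negative at baseline can count as converters in either arm, at some cost in precision and interpretability

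*Protocol*

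**What the plan says.** **Entry.** Inclusion criterion 5 (Protocol 4.1) asks that a subject "have a MAC-positive sputum at Screening". Criterion 4 asks for one further positive culture in the 6 months before Screening. No criterion concerns the Day 1 culture.

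**Interval.** Section 6.2 says of the baseline procedures: "All of the following should be performed or obtained within 70 days after Screening unless the results of the sputum culture analysis are delayed". An extension to 14 weeks is allowed when results are late. The visit-window row of Table 3-1 reads differently: "Approximately -98 to -70 (10-14 weeks".

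**Endpoint.** Section 4.6 defines a converter as a subject with "3 consecutive monthly MAC-negative sputum cultures at any time within the first 6 months of the study". Day 1 status plays no part.

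**Day 1 culture.** Section 7.1.1 requires a pre-dose specimen on Day 1. Section 3.6.1 makes a Day 1 result, positive or negative, a condition of being evaluable.

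**Analysis.** Section 9.6.1 uses the ITT population and a "Cochran-Mantel-Haenszel test stratified by smoking status and prior multi-drug regimen". The Day 1 result appears in neither the ITT nor the per-protocol definition (9.5.1, 9.5.2), nor in the strata. The 6MWT analyses in 9.6.2, by contrast, adjust for the baseline value.

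**The concern.** Culture status can change between Screening and Day 1. A subject who is negative on Day 1 and at Months 1, 2 and 3 meets the converter definition although there was no positive culture at or after the start of randomized treatment. Such subjects can appear in both arms and tell us little about LAI.

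Two things are at stake. The first is precision: conversions unrelated to treatment add variance and shrink the contrast. The second is interpretation: the reported rate mixes conversion on treatment with negativity that was already there. The information needed to separate the two is collected but not used in the primary test.

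**Working it through.** **Step 1. Reproduce the plan's figure.** Inputs from 9.1: 5% vs 20%, 2:1 allocation, two-sided 0.05, continuity-corrected chi-square. The corrected formula gives 87 control subjects, so 87 + 174 = 261, an exact match with 90.2% power. The uncorrected test at 87/174 has 93.5% power (normal approximation) or 94.6% (exact enumeration). The uncorrected figure is the fair comparison for an uncorrected CMH test.

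**Step 2. Dilution model.** Let f be the share negative on Day 1 and c the share of those who meet the converter definition, equal in both arms. If 5% and 20% hold in Day 1-positive subjects, the rate in an arm is p' = f·c + (1 − f)·p, and the difference is 0.15·(1 − f).

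- f = 5%, c = 50%: control 0.025 + 0.95 × 0.05 = 7.25%; LAI 0.025 + 0.95 × 0.20 = 21.5%; difference 14.25 points.
- f = 10%, c = 70%: control 0.07 + 0.90 × 0.05 = 11.5%; LAI 0.07 + 0.90 × 0.20 = 25.0%; difference 13.5 points.

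The difference falls only a little. Much of the power loss comes from the higher control rate and its variance, and stratifying can recover that part.

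**Step 3. Power with and without the Day 1 stratum.** Neither f nor c is in the documents, so both are assumptions, shown as ranges. The simulation used 6,000 trials per setting, two planned binary strata at an assumed 10% prevalence each, and the uncorrected CMH test at two-sided 0.05. Each cell gives planned strata → planned strata plus Day 1 culture. Monte Carlo error is about half a point on each power figure.

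| N (LAI/control) | f | c = 10% | c = 30% | c = 50% | c = 70% |
|---|---|---|---|---|---|
| 174/87 | 2% | 94.2 → 94.1 | 92.3 → 92.7 | 91.7 → 93.1 | 90.9 → 93.2 |
| 174/87 | 5% | 91.9 → 92.1 | 89.6 → 90.8 | 87.3 → 90.1 | 85.5 → 91.1 |
| 174/87 | 10% | 88.3 → 88.5 | 83.0 → 84.7 | 79.6 → 84.7 | 73.5 → 84.9 |
| 234/117 | 2% | 98.4 → 98.4 | 97.9 → 98.0 | 97.4 → 98.0 | 97.0 → 98.2 |
| 234/117 | 5% | 97.3 → 97.3 | 96.2 → 96.8 | 94.9 → 96.3 | 93.9 → 97.2 |
| 234/117 | 10% | 96.0 → 96.1 | 93.2 → 94.0 | 89.8 → 93.2 | 87.1 → 94.4 |

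At f = 0 both tests have 94.6% power at 174/87 and 98.6% at 234/117. The gain is about 0 to 11 points at 174/87 and 0 to 7 at 234/117.

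**Step 4. Alternative reading: 5% and 20% already include Day 1-negative subjects.** The rate in Day 1-positive subjects is then (p − f·c)/(1 − f). For f = 5%, c = 70%: control (0.05 − 0.035)/0.95 = 1.6%; LAI (0.20 − 0.035)/0.95 = 17.4%. Over f = 2-5% and c = 50-70% at 174/87, planned power stays at about 94%. The stratum adds about 2 to 3 points (1 to 4 across the individual settings).

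**Step 5. Type I error.** With no treatment effect, f = 5-10% and c = 50-70%, the rejection rate with the added stratum was 4.8% to 5.1% (10,000 trials per setting).

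**The case against.** The strongest case is that nothing here is an error. The CMH strata are the randomization factors, which is standard. Day 1 status is measured before dosing and balanced by randomization, so the test is valid without it. The SAP, which is not shown, may add a Day 1-positive analysis. The population is refractory, with at least two positive cultures, so f may be small. A single Day 1 negative may also be sampling variation that predicts little, and the table shows almost no gain at c = 10%. All of this stands as a limit on size. It does not remove the point, because the protocol itself fixes the strata and the converter definition.

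A reader might also infer more than the documents support:

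- **That the result is biased toward LAI.** It is not. Day 1 status is balanced in expectation and type I error holds.
- **That the control rate will exceed 5% and 261 is too few.** Section 9.1 states 5% and 20% without restricting them to Day 1-positive subjects, so they may already include the others (Step 4). The ITT population may also reach about 351 (3.6.1), that is 234/117. Losses counted as non-converters would lower the rates somewhat at that size.
- **That the Screening culture is always 10-14 weeks old.** That is the Table 3-1 wording. Sections 3.1 and 6.2 make 10 weeks the normal limit and 14 weeks an extension.
- **That the Day 1 culture may be one of the three negatives.** Section 6.3 starts the assessment at Month 3, which implies Months 1 to 3.

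**Conclusion.** The point holds as a matter of precision and interpretability. The primary endpoint can count subjects who were negative before treatment, and the primary test omits the baseline culture that would identify them. The size is not known from the documents. Under the stated assumptions the added stratum gains between nothing and about 11 power points at 174/87, and between nothing and about 7 at 234/117. The upper ends need 10% Day 1-negative with 70% of them converting. If Day 1-negatives are rare, essentially nothing is lost by adding it. The planned sample size is not shown to be wrong, and the planned test remains valid. The change is worth making because it is nearly free and the strata are fixed in this document.

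**What to change.** In 9.6.1 and the synopsis, stratify the primary CMH test by smoking status, prior multi-drug regimen and Day 1 culture (MAC-positive or MAC-negative; a missing Day 1 result counted as positive on the strength of Screening). Keep the ITT population. Use the same strata for the log-rank test of time to conversion in 9.6.2. Prespecify conversion by arm among Day 1-positive subjects as a sensitivity analysis.

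The remedy belongs in the analysis. Liquid media are held 6 weeks before a negative is reported (7.1.2), so Day 1 positivity could not be an entry condition without delaying treatment. For the same reason randomization can stay on its two factors.

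The cost is protocol and SAP wording, since the specimen is already taken. The downside is up to 8 strata instead of 4, some sparse. A stratum with only one arm, or with no variation in outcome, contributes nothing to the test. In the simulations this cost no meaningful power even at 2% Day 1-negative.

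Two minor clarifications could go in at the same time, though the point does not depend on them. One is a sentence in 4.6 that the Day 1 culture is not one of the three negatives. The other is a statement in 7.3.3.1 that the Screening isolate is the reference strain when Day 1 grew no MAC.
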